5.6 Secondary Endpoints

- Hypersensitivity
- Temporary shortness of breath
- Rarely, redness of the skin is due to heat
- Edema
- Bleeding
- Embolization
- Hematoma
- Hyperpigmentation
- Ache
- paresthesia
- Superficial thrombophlebitis
- May cause urticaria or ulcers.
- Vascular rupture and perforation
- Visible scratch
- Iatrogenic injury may damage the surrounding tissues.
- Hemothorax or pneumothorax.
- Neighboring Nerve Damage Iatrogenically
- phlebitis
- Skin Burn or discoloration

If two or more adverse effects from the above adverse effects are seen, the study is terminated.

6. Statistical Evaluation:

- According to the course of the clinical trial, if we reach the research arm (100 patients), control group (100 patients), the efficacy and safety of the treatment will be examined and an interim report will be prepared. According to the results of the interim report, the clinical trial will be terminated or the clinical trial will be continued until the number of volunteers (400 in total) mentioned above is completed.
- In this interim analysis, the patients completing the study will be evaluated considering the primary and secondary endpoints stated in the protocol and the criteria are as follows:

1-Duration in intensive care

2-Survival rate

Contribution of UVC and laser beam application to the treatment of 3-COVID 19 infection and / or superinfections accompanying COVID 19 infection

The tests to be applied are as follows:

1-Difference test between two averages for intensive care stay

(Mann-Whitney U test or t test) will be used.

2-Survival analysis tests will be used for survival rate.

Accompanying 3-COVID 19 infection treatment and / or COVID 19 infection

To investigate the contribution of UVC and laser beam application to the treatment of superinfections

Chi-square test will be applied.

Descriptive statistics will also be given for demographic data.

REFERENCE STUDIES ABOUT THE APPLICATION OF UVC BEAM "in vitro, in vivo and ex vivo"

1. The Effect of UV-C Ray Reducing Pathogen Rate on Blood Platelets Apps;

Auto-immune diseases HIV 1 -2
T-lymphotropic virus types 1 and 2
Hepatitis B (HBV)
Hepatitis C (HCV)
Hepatitis A and E
Blood pathogens (Treponema pallidum)
Parvovirus B19

With reference, UVC application, application procedures were made to reduce the amount of pathogen by preparation procedures of existing blood platelets. Platelet samples were irradiated with UV light at a wavelength of 254 nm in plastic bags (transparent) made of polyolefin acetate, and the total UVC doses applied were adjusted by irradiation time. A 1 minute irradiation time of approximately 0.4 J / cm2 was applied from both sides and the results were evaluated by two-dimensional gel electrophoresis.

Gram-positive (B. cereus, S. Aureus and S. Epidermidis) and Gram-negative bacteria (E. Coli, K. Pneumoniae, P.Aeruginosa) bacterial inactivation with UVC treatment, 5

log with dosing at $0.4 \text{ J} / \text{cm}^2$ this dose with reduced titer; found equally effective for: [2].

Sterilization of bacteria-loaded platelets; No bacterial growth was observed with a concentration of (100 CFUs / mL) cultured for 5 days, with the dose of S. Aureus and S.epidermidis 0.4 J / cm2 at a dose of [2].

UVC study of blood platelets for 7 different virus types

Tested using single-stranded (ss) RNA or DNA viruses, with or without envelopes, as well as suid herpesvirus (SHV) -1, a double-stranded (ds) DNA virus. With a slight dose of 0.4 J / cm2, the titer was reduced by 3.53 log. SHV-1 has been observed to be more resistant to UVC treatment [2].

Being more vulnerable to UVC irradiation, tested;

Small viruses (whether with or without envelopes), a decrease of 0.4 J / cm2, from 0.4 log (WNV) to 0.4 log (VSV and PPV).

HIV (a small ssRNA virus) has been observed to decrease the infectivity of this UVC dose by 1.4 log [2].

Microbiocidal and virusidal properties of UV irradiation have been known for a long time. In addition, shortwave UVC light (wavelength range 200-280 nm) has already been used for pathogen inactivation in serum, plasma and blood products such as albumin, intravenous immunoglobulins and Factor VIII concentrates [10].

Like all other pathogen inactivation methods, the advantage of the UVC technique is undoubtedly the absence of photosensitive compound, and therefore even the receiver of inactivated PCs is not exposed to a chemical compound trace. Clinically relevant G(+)and G(-) bacteria and small non-enveloped viruses are effectively inactivated. In addition, it minimizes the risk of transmission of protozoa such as Tripanosoma cruzi and Leishmania infantum and effectively inactivates Babesia divergens. The UVC method is effective for leukocyte inactivation, including T cells responsible for TA-Gvhd. Therefore, when patients at risk of developing TA-GvHD need PC transfusions, UVC irradiation is sufficient and no additional irradiation (with radiators) is required. In addition, pilot studies show that UVC irradiation not only inhibits cytokine synthesis, but also protects receptors against antigen alloimmunization. However, there are limitations such as low activity against HIV (only 1 day reduction) and increased secretion of platelet chemokines. [10].

2. Inactivating hepatitis C virus in donor lungs using light therapies during normothermic ex vivo lung perfusion

A significant number of organ donors are in the risk group for hepatitis C virus (HCV) infection. Here, studies have been carried out to evaluate the reliability and effectiveness of UVC rays in lung transplantation, where the risk of HCV transmission of UVC beam applied to the lungs before transplantation has been minimized significantly. [3].

The presence of organs is a limiting factor for lung transplantation and leads to significant mortality rates on the waiting list. The use of organs from donors with infectious viral infections such as hepatitis C virus (HCV) will increase organ donation, but these organs are generally not recommended for transplantation due to the high risk of contamination. Here, a method for the treatment of HCV infected human donor lungs that prevents transmission of HCV has been studied. In combination with germicidal light-based treatments, physical viral clearance

inactivates the HCV virus in a short time during normothermic ex-vivo Lung Perfusion (EVLP), a method for the evaluation and treatment of injured donor lungs. This treatment has been shown to be safe using a large animal EVLP-lung transplantation model. The strategy of treating viral infection in a donor organ during protection can significantly increase the availability of organs for transplantation and promote further clinical development. [3]. The UVC lamp (OSRAM Puritec® HNS 4W G5, 254 nm) or customized LED light source (centered emission at 660 nm) is placed inside the quartz tube, depending on the treatment. irradiated, UVC treatment (254 nm, 31 mW / cm², irradiation time 8 hours) applied to perfusate (flow 1 L / min) [3].

3. Inactivation of three emerging viruses - severe acute respiratory syndrome coronavirus, Crimean-Congo haemorrhagic fever virus and Nipah virus.:- in platelet concentrates by ultraviolet C light and in plasma by methylene blue plus visible light

In this study, the effectiveness of UVC beam on DNA and RNA viruses such as corona virus, crimean-congo and nipa virus, which are accepted as pandemics, were investigated. It has been observed that virus effectiveness has been made inactive by application at the rate of 20J / m2. As a result of this examination, when the samples loaded and not loaded with bacteria were examined, it was understood that the observed decrease was completely caused by UVC and MB light. The effectiveness of UVC light against single chain RNA coronavirus has been observed [4].

4. Prevention of viral transmission during lung transplantation with hepatitis C-viraemic donors: an open-label, single-centre, pilot trial

It has been observed that by using UVC light for 4-6 hours before EVLP, HCV curvature is significantly reduced in the first 7 days after transplantation. This study suggests that it may be possible to develop new strategies for routine use in clinical practice for the HVC-positive lung transplant procedure. A significant proportion of organ donors are in the risk group for hepatitis C virus (HCV) infection, where studies have been conducted to assess the safety and effectiveness of UVC rays for transplantation of the lungs, to prevent transmission of HCV to the donor organs through organ transplantation. It was able to prevent contamination. [6].

5. Potential In Vivo UVC Disinfection of Catheter lumens: Estimation of the Doses Received by the Blood Flow Outside the Catheter Tip Hole

Using UVC light sources, such as antiseptic lamps for disinfection of blood products, therapeutic treatment of whole blood and the treatment of human body or implant-related infections: Mohr and others have developed a method of pathogen inactivation for blood products using UVC irradiation. Under constant shaking with blood, he exposed it to UV light in a UV-permeable bag. They concluded that an exposure dose of 500 J / m2 resulted in an acceptable disinfection rate in their solution without sacrificing the quality of platelets. At 1500 J / m2, in vitro UVC (254 nm) irradiation of the platelet suspension layer caused a decrease in the number of platelets. UVC irradiation in biological systems has a large number of effects. The inactivation of UVC viruses and bacteria is also based on this mechanism [7].

6. Ultroviolet C lradiation for Prevention of Centrol Venous Catheter-related Infections: An in Vitro Study

With the long-term use of central venous catheters in the body or vein, a biofilm layer is seen in which microorganism development occurs between the catheter surface and the vessel wall. The

application of 254nm UVC beam applied with the help of a fiberoptic in the catheter lumen with the help of a power source has proven to significantly decrease the microorganism population (grampositive bacteria, gramnegative bacteria, fungi) present on this surface. When applying to the central venous catheter inner lumen for 60 seconds with an energy of 3.6 Joule during application, 99% microorganism inactivation was achieved. [8].

7. Ultraviolet-C Light for Treatment of Candida albicans Burn Infection in Mice

In this study, the use of 254nm UVC light was investigated for the treatment of Candida Albicans infection in third degree burns in mice. As a result of testing UVC on mouse skin, no serious damage was observed in the skin tissue and it was concluded that there was an increase in the loss of fungal lumenscence. It was concluded that UVC light therapy was effective on mice with this infection. [5]. Candida albicans is the most common fungal pathogen responsible for fungal infection in burn patients, and is the fourth most common organism found in blood cultures in intensive care unit patients.

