5.2 Inclusion Criteria

- Respiratory rate ≥ 30

- Dyspnea and breathing difficulties findings

- Cases with oxygen saturation below 90% despite nasal oxygen support of 5 liters / minute and above

- Cases with partial oxygen pressure below 70 mmHg despite nasal oxygen support of 5 liters / minute and above

- PaO2 / FiO2 <300

Lactate> 4 *mmol* / *L*

Bilateral infiltrations or multi-lobar involvement on chest x-ray or tomography

- Hypotension (systolic blood pressure <90 mmHg,> 40 mmHg drop from usual SKB, mean arterial pressure <65 mmHg)

- Skin perfusion disorder

Organ dysfunction such as kidney function test, liver function test disorder, thrombocytopenia, confusion

Presence of immunosuppressive disease-

Presence of uncontrolled comorbidity with more than one feature

- Troponin height, arrhythmia
- COVID 19 Test positivity

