5.4 Applied Treatment

5.4.1. Treatment Definition and Method

The system should be inserted into the Invamed Steerable Catheter (disposable CAMERA CATHETER) via an ultraviolet / laser light source and the fiberoptic cables connected on it. Ultraviolet / laser light from the end of the fiberoptic system destroys microorganisms (including viruses) at the end of a second-long application. The system is based on the basis of the elimination of microorganisms in these areas with a low dose of UV light / laser application from the catheter by sending it directly to the body cavities via a fresroptic catheter, intrarespiratory, intravascular (used with intracat). With the help of Invamed Steerable Catheter (Disposable Camera Catheter), UVC beam applied with a catheter inserted into the lungs and accompanying fiberoptic are interventions related to the reduction or elimination of infection. With the application of ultraviolet light / laser beam, the patient is treated with a significant reduction / destruction of the microorganism and inflammation burden in the patient's body. The proposed treatment is an antimicrobial treatment strategy, and it is recommended to combine supportive treatments with this process in terms of a holistic treatment strategy based on the clinical course of the disease. UVC and Laser application will be performed on the research arm, together with intravascular and intrarespiratory application.

Effective Dose: The blood / tissue infected with microorganism, the effective dose required to destroy the microorganism population: 2 mj / cm2 [4]

5.4.1.1. Intravascular UVC Application Process Steps:

- Hands are washed in accordance with the "Hand Hygiene and Glove Directions for Use".
- The patient is given a position in which he / she can feel comfortable according to the application area.
- A protective cover is placed under the interference area.
- Sterile Gloves are worn. IV cannula outer cover is opened.
- Fiberoptic catheter system is slowly pushed into the IV cannula.
- Approximately 5 cm cut from the tip of the catheter is adjusted to remain in the intrvascular area and UVC application is started.
- The Fiberoptic catheter is with drawn slowly after UVC administration at the specified time and strength.
- In order to apply the energy required for microorganism inactivation with the power value applied with UVC source, 200 mj / cm2 energy should be applied for 30 minutes +/- 5 minutes.

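### The Section 5.6 stopping rule ends the whole study at two of 19 listed effects, counts minor and serious effects alike, and does not define what is counted

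*Combined protocol and SAP*

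**What the plan says.** Section 5.6 of the combined protocol and SAP presents 19 adverse effects as the secondary endpoints, in one unweighted list. Some are minor, such as "Visible scratch", ache, edema, hematoma and phlebitis. Others are serious injuries, such as embolization, "Vascular rupture and perforation" and "Hemothorax or pneumothorax". The list closes with the rule: "If two or more adverse effects from the above adverse effects are seen, the study is terminated".

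Other parts of the document bear on how the rule would work:

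- **Treatment.** Section 5.4.1 says "UVC and Laser application will be performed on the research arm, together with intravascular and intrarespiratory application", for at most 5 days. For the intravascular part, "Fiberoptic catheter system is slowly pushed into the IV cannula".
- **Population.** These are intubated intensive care patients. The Section 5.2 inclusion criteria include "Organ dysfunction such as kidney function test, liver function test disorder, thrombocytopenia, confusion".
- **Other safety review.** The visit schedule has an adverse event row. Section 6 plans an interim report on efficacy and safety at 100 patients per arm, with no safety threshold. The Section 1.0 summary plans 50 patients, 25 per arm (although the words in brackets there say two hundred), while Section 6 refers to 400 in total.

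Nowhere does the text define severity grading, a causality assessment or a counting unit for the Section 5.6 rule.

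**The concern.** A stopping rule should separate events that ought to halt a trial from events that ought only to be recorded. This one does not, because every entry carries the same weight. It also leaves open whether two events, two types of effect or two patients are meant, and in which arm. Two people applying it in good faith to the same data could reach opposite decisions.

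The trial could be lost to a scratch and an ache. Equally, a single device-caused pneumothorax could leave the team with no prescribed study-level response. Minor cannulation effects are foreseeable, since device patients have intravascular and intrarespiratory procedures on up to 5 days. At 50 patients the Section 6 interim would not be reached, which leaves this sentence as the only explicit safety stop.

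**Working it through.** The plan states no operating characteristic for the rule, so there is no figure to reproduce. The check has a textual part and an illustrative part.

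**1. Literal reading.** The list runs from hypersensitivity to skin burn or discoloration and has 19 entries. The threshold is two. A visible scratch plus an ache meets it. One pneumothorax, counted as one effect, does not.

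**2. Overlapping entries.** One inflamed vein fits both phlebitis and "Superficial thrombophlebitis". One bleeding cannula site fits both bleeding and hematoma. The same holds for serious injuries: a vascular rupture also fits bleeding, hematoma and iatrogenic injury, and a hemothorax also fits bleeding. If overlapping entries both count, one event of either kind could end the trial. If each event counts once, one event of either kind ends nothing.

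**3. Relatedness.** No causality judgement is required. Thrombocytopenia at entry can itself contribute to bleeding or hematoma, and both are on the list.

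**4. Illustration.** Inputs: n = 25 device patients (Section 1.0); p = share of patients with at least one qualifying effect, assumed at 1% to 10% because no rate is documented. Let X be binomial(25, p). Then

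- P(X = 0) = (1 − p)^25
- P(X = 1) = 25 p (1 − p)^24
- P(X ≥ 2) = 1 − P(X = 0) − P(X = 1)

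At p = 5%: P(X = 0) = 0.2774, P(X = 1) = 0.3650, P(X ≥ 2) = 0.3576.

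| Assumed p | Two affected patients needed, P(X ≥ 2) | One event counted under two entries, at most P(X ≥ 1) | Exactly one affected patient, P(X = 1) |
|---|---|---|---|
| 1% | 2.6% | 22.2% | 19.6% |
| 2% | 8.9% | 39.7% | 30.8% |
| 5% | 35.8% | 72.3% | 36.5% |
| 10% | 72.9% | 92.8% | 19.9% |

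If p is the rate of serious injury and each injury counts once, the last column is the chance that one patient is injured and the rule prescribes nothing. The third and fourth columns belong to different readings and cannot both be charged to the rule.

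**5. Arm and same-patient readings.** If both arms count, at the same rates, n = 50 gives 8.9%, 26.4%, 72.1% and 96.6% for two affected patients.

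If both effects must occur in one patient, take 19 independent effects at an assumed 1% each:

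- P(a patient has at least two) = 1 − 0.99^19 − 19 × 0.01 × 0.99^18 = 0.0153.
- P(at least one such patient among 25) = 1 − (1 − 0.0153)^25, which is 31.9% before rounding.
- With the same effects, P(a patient has any) = 1 − 0.99^19 = 0.1738. If two affected patients suffice, the stopping probability is 94.7%.

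The choice of counting unit alone therefore moves the result from 31.9% to 94.7%.

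**The case against.** A low threshold is a defensible choice for an invasive device whose supporting evidence the protocol describes as in vitro, in vivo and ex vivo. An over-cautious stop errs on the side of patients. That stands, and the point here is not that two is too few. It is that the count mixes events of very different weight and is undefined.

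Relatedness is not wholly absent. The rule speaks of adverse effects, several entries carry causal wording (heat, iatrogenic injury), and the list reads mainly as device or procedure effects. It would be too strong to say that it sweeps in every intensive care event. What is missing is a formal assessment.

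The text reads as a translation, and Section 5.5 just before it defines end states for individual patients, so stopping the individual's treatment may have been intended. The words say the study, so the literal reading governs until corrected.

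Three stronger inferences are tempting and are not supported:

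- **That the rule both over-stops and under-stops on one reading of overlap.** Stopping on one minor event needs overlapping entries to count twice, whereas inaction after one serious injury needs each to count once.
- **That the rule will probably end this trial.** That depends on event rates the documents do not give.
- **That the table shows the gain from a change.** A threshold of two patients among 25 has the same binomial figures whichever events are counted. Any reduction in needless stopping depends on minor events being commoner than serious ones, which is plausible but undocumented.

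**Conclusion.** The point holds as a defect in a stated rule. The text alone establishes that two minor effects end the study, that minor and serious effects weigh the same, and that severity, formal relatedness, arm and counting unit are unstated. Whether one serious injury prescribes no action or could end the trial depends on whether overlapping entries are counted once or twice, and the text does not settle that.

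The size cannot be fixed from the documents. The probabilities rest on assumed rates, independence between patients and, in the same-patient calculation, independence between effects. They show that the outcome depends heavily on interpretation; they do not forecast this trial. The rule should be corrected before it is relied on. Confidence is medium because the sentence may have been meant at patient level.

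**What to change.** Replace the closing sentence of Section 5.6 with a study-level rule:

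1. **Unit and arm.** Count device-arm patients, each once, with a serious device- or procedure-related event.
2. **Events.** Include embolization, vascular rupture, hemothorax or pneumothorax, and serious burn, ulcer, nerve damage, bleeding or hypersensitivity. Burn, ulcer, nerve damage and hypersensitivity should not be treated as minor by default for a UVC and laser device.
3. **First event.** Pause enrolment for safety review after any single such event.
4. **Termination.** Terminate at two such patients, unless the safety reviewers set another count against the number treated. State the operating characteristics. For 25 patients at true serious-event rates of 1%, 2%, 5% and 10%, termination at two occurs 2.6%, 8.9%, 36% and 73% of the time, and the single-event pause 22%, 40%, 72% and 93%. The pause therefore carries much of the protection.
5. **Minor events.** Record them and compare them by arm, without triggering termination.

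If the sentence was meant to stop an individual patient's treatment, say so and add the study-level rule above.

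The cost is protocol wording, a short calculation and agreement on the event list and count with the safety reviewers. The downsides are that relatedness must be judged for each event, single-event pauses may interrupt recruitment, and the trial no longer stops automatically on minor events.

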1.0 SUMMARY of INVESTIGATION

Study Title:	Prospective, Parallel, Multicenter Randomized Controlled Study Investigating the Effects of UVC Beam and Laser Beam Therapy According to Standard Therapy in Patients with Covid-19 Diagnosis
Study Code:	MD2020/001
Device :	Turkishbeam Model Number: 1007-001
	*: The device was produced by RD GLOBAL ARASTIRMA GELISTIRME SAĞLIK ILAÇ INSAAT YATIRIMLARI A.S.
Device Classification:	Class III
Purpose of the Study:	Clinical research study that evaluates the effect of Turkish Beam- Selective UV developed by RD GLOBAL ARASTIRMA GELISTIRME SAĞLIK ILAÇ INSAAT YATIRIMLARI A.S. use into Intravascular, Intrapulmonary, Intratracial, Intrarespiratory area. Bacteria, Fungal and Virus-based pathogens systematically to collect and evaluate specific clinical performance and safety data. In our Clinical Research, we aimed to investigate the effectiveness of the treatment group and control group mortality rates, intensive care hospitalization times, monitoring the virus load by PCR, and the treatment effectiveness of UVC

Scope of the Study:	This Clinical Research covers determining the treatment effectiveness and reliability of UVC application to patient groups, the details of which are determined in the protocol.
Application:	Intravascular, Intrapulmonary, Intratracial, Intrarespiratory UVC and Laser Therapy System
Overall Study Design:	Prospective, Parellel, Multicenter, Randomized Controlled
Number of volunteers:	50 patient- 2 groups with 25 (two hundred) patients in each group
Treatment Groups:	Test: Antiviral + Antimalarial + Antibiotic Treatment + UVC Therapy Control: Antiviral + Antimalarial + Antibiotic Treatment
Groups of Volunteer:	Those who are between the ages of 40-75 and who have applied to the clinic with symptoms such as fever, weakness, cough, and shortness of breath, or who have signs of COVID-19 (SARS- CoV-2) test positive or atypical pneumonia findings in CT findings and accepted as COVID 19 infection, and patients undergoing intubation treatment in intensive care unit
Sensitive population / Vulnerable subjects:	The study will not include under-40, pregnant women and those with suspected pregnancy, previously diagnosed with mental disorders, puerperant women and lactating women

Duration of the clinical trial: 3 months (04.2020- 07.2020)

Researched Medical Condition:

and Disease

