4.7 Selective Permeable Effective Ultraviolet Wavelength Determination to be Applied

The ultraviolet C (UVC) beam is an alternative methods to existing methods used in the treatment of localized infections. Some drug resistant microorganisms have also been found to be sensitive to UVC irradiation. UV radiation can kill all kinds of microorganisms with its short wavelength and high energy. The greatest antimicrobial activity is in the wavelength region of 250-264 nm.

Contrary to what is known, UVC, selected with appropriate doses, can selectively inactivate microorganisms while maintaining the viability of mammalian cells and has also been proven to promote wound healing. UVC (200nm - 280 nm) has been proven to cause less damage to tissue than UVB in animal studies. [one]. Although UVC can cause DNA damage in mammalian cells, it can be quickly repaired by DNA repair enzymes. [one]. In summary, UVC is an innovative treatment method of our age as an alternative approach to existing methods used for localized infections, single stranded RNA and double stranded DNA viruses, especially for the treatments caused by highly antibiotic-resistant microorganisms. UVC should be used in such a way that side effects are minimized and the resistance of microorganisms to UVC is prevented.

4.8 Benefits / Risks:

Risks from implementation:

-Vascular rupture

- -If the guide cannula moves out of the target, tissue damage and radiation-related damage
- -Depending on the place of application, thrombosis

-Pulmonary tissue damage

- -Pnomotoraks
- -Hemotoraks

Risks from the beam device: Retinal damage and vision loss

The risks mentioned above are due to the fact that the work team is selected from experienced and competent people.

has been minimized. They will also undergo a separate training for applications. Already intensive care and intubation in intratracheal / pulmonary / intravascular interventions In addition to the risks that may occur under the

It stands out.

On the other hand, it is compulsory to use ultraviolet-proof glasses as specified in the protocol for the patient who performs the application. There is no additional risk that may arise from the device.

However, the benefit that will arise from beam application is very high compared to these risks.

With the treatment we envisaged, survival will increase significantly.

We think that the duration will be shortened and superinfections will be prevented. Summarized benefit / risk

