5.0 METHODOLOGY

5.1 Patient Admission Criteria (Diagnosis / Medical Table)

Symptoms such as fever, weakness, cough, mild shortness of breath between the ages of 40-75 referring to the clinic with COVID-19 (SARS-CoV-2) test positive or atypical in CT findings. Patients with signs of pneumonia and considered COVID 19, undergoing intubation treatment in the intensive care unit, and meeting the inclusion / exclusion criteria. Patients who are not found suitable according to the intervals specified in the Inclusion / Exclusion criteria will not be included in the study.

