Adverse Event		X	X	X	X	X	X	X
Concomitant Therapy (UVC)			x	x	x	X	x	x
PCR sampling			X		X		X	X
Serum Antibody Level			1					X

Following the improvement of the clinical course of the patients, it is planned to take the patient's serum plasma on the 7th and 15th days, and to test and store it under suitable conditions for the antibody test.

Blood tests to be performed: Complete blood count, urea, creatinine, sodium, IL-1 β , IL-6, TNF α , TGF β potassium, chlorine, AST, ALT, total bilirubin, LDH, CPK, D-dimer, troponin, Ferritin, fibrinogen, procalcitonin, CRP values, quantitative measurement of PCR results of the source of infection

Radiological Imaging: Chest X-ray and / or Lung CT is taken. Clinical decision should be made according to history and examination findings in patients who cannot have chest X-ray and / or lung CT. (Radiological findings: Consolidation, ground glass appearance and reticulo-nodular opacity

appearance should be investigated in lung CT. Signs of pneumonia in lung graphy should be examined.)

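### Read literally, the section 5.6 stopping rule counts any listed effect in either arm, including Day 0 findings and background ICU events, and does not fix its counting unit

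*Combined protocol and SAP*

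**What the plan says.** The rule is the last sentence of section 5.6 (Secondary Endpoints), after 19 bulleted effects: "If two or more adverse effects from the above adverse effects are seen, the study is terminated". No other sentence in the combined protocol and SAP explains how to apply it.

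The bullets are of two kinds.
- Some name or imply a cause in the application: "Rarely, redness of the skin is due to heat", "Iatrogenic injury may damage the surrounding tissues", the iatrogenic nerve damage item and the skin burn item.
- Others name no cause: "Temporary shortness of breath", edema, bleeding, hematoma, ache, phlebitis.

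Section 4.8 (Benefits / Risks) has its own list under "Risks from implementation". It shares vascular rupture, pneumothorax and hemothorax with 5.6 and gives no procedure for attributing an event.

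Section 5.1 admits patients "undergoing intubation treatment in the intensive care unit". The inclusion criteria in 5.2 name dyspnea and thrombocytopenia.

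The follow-up table in 5.4.1 has an "Adverse Event" row marked from randomisation on Day 0 to the Day 7 and 15 follow-up. UVC is first marked on Day 1.

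Section 1.0 gives the size as "50 patient- 2 groups with 25 (two hundred) patients in each group", and section 6 speaks of 400 in total.

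**The concern.** A rule that ends a trial has to separate harm from the treatment from what would have happened anyway. The only input here is that listed effects are seen. Several of them can be expected in ventilated intensive care patients without any device, and some overlap the entry criteria: shortness of breath with dyspnea, bleeding and hematoma with thrombocytopenia. Taken literally, a finding already present on Day 0, or an event in a control patient, counts as much as an injury from the catheter.

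Two things are at stake. The trial could be ended by background events, leaving its question unanswered. And two centres could follow the same sentence differently, because two or more can mean patients, occurrences or types, and the scope can be read as the trial or as one patient's participation.

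**Working it through.** **No plan figure to reproduce.** The documents give no expected event rate and no operating characteristic for the rule.

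**Inputs**
- Threshold: two or more (5.6).
- Size: n = 25 for the UVC arm, n = 50 for both arms (1.0).
- Background rate p: the probability that a patient has at least one listed effect from disease or routine care. It is not in the documents. Assumed 2%, 5% and 10%, independent between patients.
- No device effect, unless stated.

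**Reading A: two or more affected patients**

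P(stop) = 1 − (1−p)^n − n·p·(1−p)^(n−1)

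At p = 5%:
- n = 25: 1 − 0.277 − 0.365 = 0.358
- n = 50: 1 − 0.077 − 0.202 = 0.721

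| p | n = 25 | n = 50 |
|---|---|---|
| 2% | 9% | 26% |
| 5% | 36% | 72% |
| 10% | 73% | 97% |

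With the 400 patients of section 6 the figure is 91% even at p = 1%.

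**Reading B: two types of effect in the same patient**

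Further assumption: six background-prone types, independent and equally frequent, giving the same p. The per-type rate is q = 1 − (1−p)^(1/6). The chance of two or more types in one patient is c = P(Bin(6, q) ≥ 2). Then P(stop) = 1 − (1−c)^n.

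At p = 5%, q = 0.0085 and c = 0.00106, so n = 25 gives 0.026 and n = 50 gives 0.052.

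| p | n = 25 | n = 50 |
|---|---|---|
| 2% | 0.4% | 0.8% |
| 5% | 2.6% | 5% |
| 10% | 10% | 20% |

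Using 3 or 10 types instead of 6 at p = 5% gives 2.1% or 2.8% for n = 25. If effects cluster within patients, these figures would be higher.

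**Reading C: only that patient's participation ends.** No trial-level figure applies.

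**Effect of filtering the patient count (n = 25).** Suppose filters leave a share f of background events countable. Use Reading A at rate f·p for false stops. For real harm, suppose UVC adds events at rate p, all of which count: the current rule then works at rate 2p and the filtered count at f·p + p.

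| | p = 2% | p = 5% | p = 10% |
|---|---|---|---|
| False stop, current | 9% | 36% | 73% |
| False stop, f = 0.5 | 2.6% | 13% | 36% |
| False stop, f = 0.2 | 0.4% | 2.6% | 9% |
| Stop under real harm, current | 26% | 73% | 97% |
| Stop under real harm, f = 0.5 | 17% | 57% | 91% |
| Stop under real harm, f = 0.2 | 12% | 45% | 82% |

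The shares f are assumptions. The rows describe the patient count alone and leave out any separate trigger for a single serious event.

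**A single-event trigger.** If one unfiltered serious event ended the trial, the false-stop chance in 25 patients would be 1 − 0.99^25 = 22% at an assumed 1% combined background rate, and 1 − 0.98^25 = 40% at 2%.

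**The case against.** The strongest reply is that the literal reading is not the natural one. The rule speaks of adverse effects, whereas the schedule records adverse events. The list reads like a device's catalogue of possible effects, with heat, burn and iatrogenic items, and it overlaps 4.8. Effects of the application can arise only in the UVC arm. This stands as evidence of intent. It does not supply what is missing: most bullets name no cause, and nobody is told to judge it.

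The schedule also provides a collection window. It does, but the rule does not refer to it, and the window opens on Day 0, before the first application.

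A very sensitive stop is a defensible choice for an invasive Class III device, and filtering by cause costs sensitivity. That stands too. No blinding is described, and 4.8 already denies any additional risk from the device, so a strict relatedness test could under-attribute harm. This bears on how the filter is worded; it does not justify counting control-arm or Day 0 findings.

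The illustrations rest on assumed rates. Shortness of breath and ache are also hard to observe in sedated, intubated patients, so signs visible to staff would carry most of the background.

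From the larger percentages a reader might infer that the trial will probably be stopped falsely. The documents do not support that: they give no background rate, and across the readings and rates tabulated for the current rule the chance runs from 0.4% to 97%.

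**Conclusion.** The concern holds for the literal, trial-wide reading. As written, the rule counts any listed effect in either arm, whether present at Day 0 or caused by the disease or by intensive care, and leaves the counting unit open. That is a fault in the rule as well as a gap in detail, because following the sentence exactly can end the trial with no device effect. On the other readings it is ambiguous. It should be fixed.

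The size is illustrative and depends most on the unit. At an assumed p of 5% in the UVC arm, the false-stop chance is 36% for two affected patients and 2.6% for two types in one patient. These figures assume independence between patients and the sizes in section 1.0.

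Two further inferences go beyond the documents. One is that the sponsor meant to count effects regardless of cause; the list and 4.8 point the other way. The other is that the percentages for the filtered count are the performance of a complete amended rule; they are not.

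**What to change.** Amend the last sentence of 5.6 and add one table.

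1. **What counts.** A listed effect in a UVC-arm patient that is new or worse than that patient's Day 0 record, starts after the first Day 1 application, and is not clearly explained by another cause. If in doubt, it counts; this limits under-attribution in a trial with no described blinding.
2. **Unit and scope.** State that the unit is patients and the scope is the trial: two or more UVC-arm patients with a qualifying effect. The threshold number stays with the sponsor and the safety clinicians, and a deliberately sensitive one is acceptable.
3. **Serious procedure events.** If vascular rupture, hemothorax or pneumothorax, or embolization is given a single-event trigger, apply the same filters and make the action a pause with a safety review, not automatic termination.
4. **Reporting.** Tabulate each listed event by arm as patients affected over patients randomised, with the risk difference and 95% CI.

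The cost is protocol wording and one safety table. No new visits are needed, since examination, vital signs and adverse events are already scheduled on Day 0 and each treatment day. The downsides are that investigators must judge cause and worsening, and that the count is somewhat less sensitive to true harm: at p = 5% with a doubled rate, 57% or 45% instead of 73% under the assumed shares. Letting doubtful cases count would leave more background events in the count and reduce that loss.
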